**Table 5. Specific Toxicity Management Guidelines for Abnormal Laboratory Values (Continued)**

Laboratory Parameter	Toxicity Management Guideline
AST or ALT	
 
• Interrupt study drug immediately if confirmed ALT or AST > 3 × ULN by repeat testing with new sample and either a total bilirubin > 2 × ULN or an international normalized ratio > 1.5.               
 
○ A separate blood sample for INR testing will be needed to measure INR at the time of repeat testing for ALT or AST. A repeat test of INR is not needed for determination if above toxicity management criteria are met.
 
 
 
• Interrupt study drug immediately if confirmed ALT or AST > 3 × ULN by repeat testing with new sample along with appearance of fatigue, nausea, vomiting, right upper quadrant pain or tenderness, fever, rash, and/or eosinophilia (> 5%).
 
• Interrupt study drug immediately if confirmed ALT or AST > 5 × ULN by repeat testing with new sample for more than 2 weeks.
 
• If ALT or AST > 8 × ULN, interrupt study drug immediately, confirm by repeat testing with a new sample and contact the TAMD.
 
 
Subjects who meet any of the above criteria should be evaluated for an alternative etiology of the ALT or AST elevation and managed as medically appropriate. If applicable, the alternative etiology should be documented in the eCRF. If ALT or AST values return to the normal reference range or its Baseline value, study drug may be restarted. If restarting study drug, documentation should include reason that rechallenging is expected to be safe. If after clinically appropriate evaluation, no alternative etiology for ALT or AST elevation is found or the ALT or AST elevation has not resolved or is not trending down toward normal, the subject should be discontinued from study drug
 
 
• For subjects with HBc Ab+ (irrespective of HBs Ab status) and negative HBV DNA at screening who develop the following should have HBV DNA by PCR testing performed within one week:               
 
○ ALT > 5 × ULN OR
 
○ ALT or AST > 3 × ULN if an alternative cause is not readily identified.
 
 
 
• A positive result for HBV DNA PCR testing in these subjects will require immediate interruption of study drug and a hepatologist consultation should occur within one week for recommendation regarding subsequent treatment.
 
 
For any confirmed ALT or AST elevations > 3 ULN, complete supplemental hepatic eCRF.

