**Table 5. Specific Toxicity Management Guidelines for Abnormal Laboratory Values**

Laboratory Parameter	Toxicity Management Guideline
Hemoglobin	
 
• If hemoglobin < 8 g/dL, interrupt study drug dosing and confirm by repeat testing with new sample.
 
• If hemoglobin decreases <math>\geq 3.0</math> g/dL from baseline without an alternative etiology, interrupt study drug dosing and confirm by repeat testing with new sample.
 
• If hemoglobin decreases <math>\geq 3.0</math> g/dL from baseline and an alternative etiology is known, the subject may remain on study drug at the investigator's discretion.
 
• If confirmed, continue to withhold study drug until hemoglobin value returns to normal reference range or its baseline value.
 

Absolute neutrophil count (ANC)	
 
• If confirmed < 1,000/<math>\mu</math>L, interrupt study drug dosing until ANC value returns to normal reference range or its Baseline value.
 
• Discontinue study drug if confirmed < 500/<math>\mu</math>L by repeat testing with new sample.
 

Absolute lymphocytes counts (ALC)	
 
• If confirmed < 500/<math>\mu</math>L by repeat testing with new sample, interrupt study drug dosing until ALC returns to normal reference range or its Baseline value.
 

Total white blood cell count*	
 
• If confirmed < 2,000/<math>\mu</math>L by repeat testing with new sample, interrupt study drug dosing until white blood cell count returns to normal reference range or its Baseline value.
 

Platelet count	
 
• If confirmed < 50,000/<math>\mu</math>L by repeat testing with new sample, interrupt study drug dosing until platelet count returns to normal reference range or its Baseline value.
 

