
**Table 5. Specific Toxicity Management Guidelines for Abnormal Laboratory Values (Continued)**

Laboratory Parameter	Toxicity Management Guideline
Serum Creatinine	
 
If serum creatinine is <math>> 1.5 \times</math> the baseline value and <math>> \text{ULN}</math>, repeat the test for serum creatinine (with subject in an euvoletic state) to confirm the results. If the results of the repeat testing still meet this criterion, then interrupt study drug and re-start study drug once serum creatinine returns to <math>\leq 1.5 \times</math> baseline value and <math>\leq \text{ULN}</math>
 
If confirmed serum creatinine <math>\geq 2 \text{ mg/dL}</math>, interrupt study drug and re-start study drug once serum creatinine returns to normal reference range or its baseline value.
 
For the above serum creatinine elevation scenarios, complete supplemental renal eCRF.
 

Creatine Phosphokinase	
 
If confirmed CPK value <math>\geq 4 \times \text{ULN}</math> and there are no symptoms suggestive of myositis or rhabdomyolysis, the subjects may continue study drug at the investigator's discretion.
 
If CPK <math>\geq 4 \times \text{ULN}</math> accompanied by symptoms suggestive of myositis or rhabdomyolysis, interrupt study drug and contact AbbVie Therapeutic Area Medical Director.
 
For the above CPK elevation scenarios, complete supplemental CPK eCRF.
 

\* Local requirements may apply. Refer to [Appendix N](#) for local requirements (United Kingdom).

If the subject must undergo elective surgery, the study drug should be interrupted at least 1 week prior to the surgery. If the subject must undergo emergency surgery, the study drug should be interrupted at the time of the surgery. The study drug can recommence once the physician has examined the surgical site and determined that it has healed and there is no sign of infection.

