**Table 5. Specific Toxicity Management Guidelines for Abnormal Laboratory Values**

Laboratory Parameter	Toxicity Management Guideline
Hemoglobin	
 
• If hemoglobin < 8 g/dL, interrupt study drug dosing and confirm by repeat testing with new sample.
 
• If hemoglobin decreases <math>\geq</math> 3.0 g/dL from baseline without an alternative etiology, interrupt study drug dosing and confirm by repeat testing with new sample.
 
• If hemoglobin decreases <math>\geq</math> 3.0 g/dL from baseline and an alternative etiology is known, the subject may remain on study drug at the investigator's discretion.
 
• If confirmed, continue to withhold study drug until hemoglobin value returns to normal reference range or its baseline value.
 

Absolute neutrophil count (ANC)	
 
• If confirmed < 1,000/<math>\mu</math>L, interrupt study drug dosing until ANC value returns to normal reference range or its Baseline value.
 
• Discontinue study drug if confirmed < 500/<math>\mu</math>L by repeat testing with new sample.
 

Absolute lymphocytes counts	
 
• If confirmed < 500/<math>\mu</math>L by repeat testing with new sample, interrupt study drug dosing until ALC returns to normal reference range or its Baseline value.
 

Total white blood cell count	
 
• If confirmed < 2,500/<math>\mu</math>L by repeat testing with new sample, interrupt study drug dosing until white blood cell count returns to normal reference range or its Baseline value.
 

Platelet count	
 
• If confirmed < 50,000/<math>\mu</math>L by repeat testing with new sample, interrupt study drug dosing until platelet count returns to normal reference range or its Baseline value.
 

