**Table 5. Specific Toxicity Management Guidelines for Abnormal Laboratory Values (Continued)**

Laboratory Parameter	Toxicity Management Guideline
AST or ALT	
 
• Interrupt study drug immediately if confirmed ALT or AST <math>> 3 \times</math> ULN by repeat testing with new sample and either a total bilirubin <math>> 2 \times</math> ULN or an international normalized ratio <math>> 1.5</math>.               
 
○ A separate blood sample for INR testing will be needed to measure INR at the time of repeat testing for ALT or AST. A repeat test of INR is not needed for determination if above toxicity management criteria are met.
 
 
 
• Interrupt study drug immediately if confirmed ALT or AST <math>> 3 \times</math> ULN by repeat testing with new sample along with appearance of fatigue, nausea, vomiting, right upper quadrant pain or tenderness, fever, rash, and/or eosinophilia (<math>> 5\%</math>).
 
• Interrupt study drug immediately if confirmed ALT or AST <math>> 5 \times</math> ULN by repeat testing with new sample for more than 2 weeks.
 
• Interrupt study drug immediately if confirmed ALT or AST <math>> 8 \times</math> ULN by repeat testing with new sample.
 
 
Subjects who meet any of the above criteria should be evaluated for an alternative etiology of the ALT or AST elevation and managed as medically appropriate. If applicable, the alternative etiology should be documented in the eCRF. If ALT or AST values return to the normal reference range or its Baseline value, study drug may be restarted. If restarting study drug, documentation should include reason that rechallenge is expected to be safe. If after clinically appropriate evaluation, no alternative etiology for ALT or AST elevation found or the ALT or AST elevation has not resolved or is not trending down toward normal, the subject should be discontinued from study drug.
 
For any confirmed ALT or AST elevations <math>> 3</math> ULN, complete supplemental hepatic eCRF.
 
 
• For Subjects with HBc Ab+ (irrespective of HBs Ab status) and negative HBV DNA at screening who develop the following should have HBV DNA by PCR testing performed within one week:               
 
○ ALT <math>> 5 \times</math> ULN OR
 
○ ALT or AST <math>> 3 \times</math> ULN if an alternative cause is not readily identified.
 
○ A positive result for HBV DNA PCR testing in these subjects will require immediate interruption of study drug and a hepatologist consultation should occur within one week for recommendation regarding subsequent treatment.
 
 
 
 
For any confirmed ALT or AST elevations <math>> 3</math> ULN, complete supplemental hepatic eCRF.

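### For ALT or AST above 8 × ULN, the main Table 5 and the UK Table 5 in Appendix N give different instructions, and the protocol does not say which one governs UK subjects

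*Protocol*

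**What the plan says.** The protocol contains two tables numbered and titled Table 5, both setting out toxicity management for abnormal laboratory values. One is in Section 6.10. The other is in Appendix N (Local Requirements), under United Kingdom.

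For ALT or AST above 8 × ULN, the Section 6.10 table says to "interrupt study drug immediately, confirm by repeat testing with a new sample and contact the TAMD". The Appendix N table says "Interrupt study drug immediately if confirmed ALT or AST > 8 \times ULN by repeat testing with new sample" and stops there, with no contact step in that bullet.

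The Section 6.10 table has an asterisk for local differences. Its footnote begins "Local requirements may apply. Refer to" and points to Appendix N for the United Kingdom. The only row that carries the asterisk is "Total white blood cell count".

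The text of Section 6.10 that introduces Table 5 requires confirmation by repeat testing and wants any repeat done as soon as possible. It does not say whether interruption comes before or after confirmation.

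**The concern.** Two current safety instructions in one protocol prescribe different actions for the same laboratory value. A UK investigator who works from Section 6.10 sees no local flag on the ALT/AST row and would interrupt on the first value and contact the medical director. One who works from Appendix N would wait for confirmation before the rule requires interruption, and would find no contact step in that bullet.

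This trigger has the highest ALT/AST multiple in the table, and Section 6.4 lists hepatic events and raised transaminases as adverse events of special interest. Two things are at stake for a UK subject who crosses the threshold: whether drug continues while the repeat is awaited, and whether the sponsor's medical director is told. There is also a compliance question. Section 7.0 gives an incorrect dose as an example of a protocol deviation, and a site can be judged on its dosing only if it knows which rule it was meant to follow.

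**Working it through.** No arithmetic applies. The check is a row-by-row comparison of the two tables, then a look at where the local-requirement flag is used.

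**Step 1. The bullet for ALT or AST above 8 × ULN.**

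| Item | Section 6.10, Table 5 | Appendix N (UK), Table 5 |
|---|---|---|
| What triggers interruption | First value | Confirmed value |
| Repeat test on a new sample | After interruption | Before interruption |
| Contact with the medical director | Stated | Not stated |

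**Step 2. The other rows.**
- Hemoglobin, neutrophils, lymphocytes, platelets, creatinine and CPK: same thresholds and actions in both tables.
- The other three ALT/AST interruption bullets, and the hepatitis B testing instructions: same in both.
- White cells: below 2,000/µL in the main table, below 2,500/µL in the UK table.

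There are thus two substantive differences, the white cell threshold and the rule above 8 × ULN.

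**Step 3. Which differences are flagged.**
- White cell row: asterisk present, and the UK threshold does differ.
- Laboratory exclusion criterion 4 (Section 5.2.2 and the synopsis): asterisk present, and Appendix N supplies a different UK criterion.
- ALT/AST row: no asterisk, although the UK instruction differs.

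The flag is used for the other two UK differences examined and is missing for this one.

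**Step 4. Does anything else settle which row governs?**
- Appendix N does not say that its Table 5 replaces the main table in full, nor that it applies only where flagged.
- The introduction to Table 5 is silent on the order of interruption and confirmation.
- The UK table has no uniform pattern that would explain the difference. Its hemoglobin row interrupts first and then confirms, as the main table does, and its CPK row keeps the contact with the medical director. On the other hand, confirming first is the pattern of the other three ALT/AST interruption bullets in both tables.

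None of this decides the matter. The text supports either reading.

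**The case against.** The strongest reply is that Appendix N is headed as local requirements for the United Kingdom and reprints every row, so a UK site may properly treat the whole table as its own. On that view the difference is presented as local and merely lacks a cross-mark in the main row. This is a fair reading, but the documents do not establish it. The main table sends the reader to Appendix N only from the white cell row.

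A reader might go further and infer that all UK subjects above 8 × ULN stay on drug while others stop, and that UK sites are not told to make the contact. The documents do not support this. It holds only if Appendix N replaces the main row. If the asterisk limits Appendix N to the flagged row, the main ALT/AST rule applies in the UK with immediate interruption and contact. Even under Appendix N, the repeat is due as soon as possible, the investigator must assess the subject and apply standard of care (Section 6.10), and may discontinue a subject for safety concerns (Section 5.4.1). Nothing in the UK bullet forbids earlier interruption. These points limit the effect but leave the conflict in place.

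A reader might also infer from the summary of changes in Section 1.1 that the UK bullet is an outdated copy. That cannot be concluded. The entry concerns the contact step and does not say that the order of interruption and confirmation changed. Section 1.1 also lists separate UK-only amendments, and their content and reasons are not shown. Whether the UK wording is deliberate cannot be determined.

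**Conclusion.** The inconsistency is real. For the same laboratory value, two current tables differ on the order of interruption and confirmation and on contact with the medical director, and nothing in the protocol says which governs UK subjects.

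Its size cannot be put in numbers. The documents give neither the number of UK subjects nor the turnaround of a repeat test. The consequence is conditional: if Appendix N governs, a UK subject above 8 × ULN could remain on drug until the repeat result, and the contact step would not apply; if the main row governs, there is no such effect.

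No planned analysis changes. SAP Sections 10.3.4 and 10.3.5 grade and count liver values by threshold, whether or not drug was interrupted. The point therefore concerns clarity of safety conduct, not the validity of a result. The conclusion rests only on the current wording of the two tables and the placement of the asterisk.

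**What to change.** Reconcile the ALT/AST bullets above 8 × ULN in Section 6.10 Table 5 and Appendix N Table 5 on two items: the order of interruption and confirmation, and the contact with the medical director. If a UK difference is intended, put the Appendix N asterisk on the main ALT/AST row, as is done for white cells. The choice of rule is for the sponsor and its medical advisers, and none is proposed here.

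The cost is a clarifying letter to UK sites or one line in the next UK amendment. No data collection or analysis needs to change.

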
**Table 5. Specific Toxicity Management Guidelines for Abnormal Laboratory Values (Continued)**

Laboratory Parameter	Toxicity Management Guideline
Serum Creatinine	
 
If serum creatinine is <math>> 1.5 \times</math> the baseline value and <math>> \text{ULN}</math>, repeat the test for serum creatinine (with subject in an euvoletic state) to confirm the results. If the results of the repeat testing still meet this criterion, then interrupt study drug and re-start study drug once serum creatinine returns to <math>\leq 1.5 \times</math> baseline value and <math>\leq \text{ULN}</math>
 
If confirmed serum creatinine <math>\geq 2 \text{ mg/dL}</math>, interrupt study drug and re-start study drug once serum creatinine returns to normal reference range or its baseline value.
 
For the above serum creatinine elevation scenarios, complete supplemental renal eCRF.
 

Creatine Phosphokinase	
 
If confirmed CPK value <math>\geq 4 \times \text{ULN}</math> and there are no symptoms suggestive of myositis or rhabdomyolysis, the subjects may continue study drug at the investigator's discretion.
 
If CPK <math>\geq 4 \times \text{ULN}</math> accompanied by symptoms suggestive of myositis or rhabdomyolysis, interrupt study drug and contact AbbVie Therapeutic Area Medical Director.
 
For the above CPK elevation scenarios, complete supplemental CPK eCRF.
 

\* Local requirements may apply. Refer to [Appendix N](#) for local requirements (United Kingdom).

If the subject must undergo elective surgery, the study drug should be interrupted at least 1 week prior to the surgery. If the subject must undergo emergency surgery, the study drug should be interrupted at the time of the surgery. The study drug can recommence once the physician has examined the surgical site and determined that it has healed and there is no sign of infection.

## 6.11 Cardiovascular Adjudication Committee

An independent committee of physician experts in cardiovascular adjudication will be utilized to assess cardiovascular and embolic and thrombotic (non-cardiac, non-CNS) adverse events as defined by the Cardiac Adjudication Committee charter.

## 6.12 Product Complaint

### 6.12.1 Definition

A Product Complaint is any Complaint (see Section 6.1 for the definition) related to the biologic or drug component of the product.

For a product this may include, but is not limited to, damaged/broken product or packaging, product appearance whose color/markings do not match the labeling, labeling discrepancies/inadequacies in the labeling/instructions (example: printing illegible), missing components/product, or packaging issues.

Any information available to help in the determination of causality to the events outlined directly above should be captured.

### **6.12.2 Reporting**

Product Complaints concerning the investigational product must be reported to the Sponsor within 24 hours of the study site's knowledge of the event via the Product Complaint form. Product Complaints occurring during the study will be followed-up to a satisfactory conclusion. All follow-up information is to be reported to the Sponsor (or an authorized representative) and documented in source as required by the Sponsor. Product Complaints associated with adverse events will be reported in the study summary. All other complaints will be monitored on an ongoing basis.

Product Complaints may require return of the product with the alleged complaint condition. In instances where a return is requested, every effort should be made by the Investigator to return the product within 30 days. If returns cannot be accommodated within 30 days, the site will need to provide justification and an estimated date of return.

The description of the complaint is important for AbbVie in order to enable AbbVie to investigate and determine if any corrective actions are required.

## **7.0 Protocol Deviations**

AbbVie does not allow intentional/prospective deviations from the protocol. The principal investigator is responsible for complying with all protocol requirements, and applicable global and local laws regarding protocol deviations. If a protocol deviation occurs (or is identified, including those that may be due to the COVID-19 or any pandemic or any state of emergency situation) after a subject has been enrolled, the

principal investigator is responsible for notifying Independent Ethics Committee (IEC)/Independent Review Board (IRB) regulatory authorities (as applicable), and their assigned clinical monitor, or AbbVie representative, or the following AbbVie clinical study team contact(s):

Primary Contact:

[REDACTED]  
[REDACTED]  
[name]  
[REDACTED]  
[name]

Office:  
Cell:  
Fax:  
Email:

[REDACTED]

Such contact must be made as soon as possible to permit a review by AbbVie to determine the impact of the deviation on the subject and/or the study.

Examples of protocol deviations include the following:

- Subject entered into the study even though she/he did not satisfy entry criteria
- Subject who developed withdrawal criteria during the study and was not withdrawn
- Subject who received wrong treatment or incorrect dose
- Subject who received excluded or prohibited concomitant treatment

## **8.0 Statistical Methods and Determination of Sample Size**

### **8.1 Statistical and Analytical Plans**

#### **8.1.1 Dataset for Analysis**

The analysis set consists of all subjects who enrolled into this OLE study and received at least one dose of open-label study medication upadacitinib. This analysis set will be the primary analysis population for both efficacy and safety evaluation.

#### **8.1.2 Subject Accountability**

The number of subjects who received at least one dose of study drug, the number of subjects who completed the study, and the number of subjects who prematurely discontinued will be calculated overall and for each investigational site.

#### **8.1.3 Baseline Characteristics**

For analyses purposes, baseline data for each subject will be the data collected at the visit immediately prior to starting double-blind treatment. In an alternate assessment for summarizing the safety and laboratory data, baseline data will be assumed to be the data collected at the visit immediately prior to starting treatment with active upadacitinib.

Demographic variables such as age, gender, race, height, weight, BMI, race, ethnicity, duration of disease, vital signs (blood pressure, heart rate, and temperature), and planned efficacy assessments such as the counts for both SJC and TJC, Patient's Assessment of Pain (VAS), Patient's Global Assessment of Disease Activity, Physician's Global Assessment of Disease Activity, Patient's Assessment of Physical Function by Health Assessment Questionnaire – Disability Index (HAQ-DI), and hsCRP will be summarized at Baseline.

Summary statistics for continuous variables will include the number of observations, mean, standard deviation, median, and range. For other discrete variables, frequencies and percentages will be computed in each category.

